The failure to use isoniazid (INH) preventative therapy (IPT) in HIV-infected individuals in Sub-Saharan Africa represents one of the single biggest implementation gaps between evidence and practice in today's response to the HIV epidemic. IPT reduces TB incidence by 40%.^{1,2} Yet today, in Africa, less than 2% of eligible individuals receive IPT³ and TB remains the largest killer of HIV-infected persons.⁴ Given the existence of both clear guidelines recommending IPT from international organizations and national health ministries in Africa, as well as simple symptom-based clinical algorithms for identifying persons eligible for IPT that can be applied by front line health care workers,⁵ a remaining critical requirement for IPT scale-up is strengthening the link – mediated by middle management in most health systems – between health ministry policy and clinics.

In the Republic of Uganda, the 112 local District Health Officers (DHOs) are the highest-ranking health officials based in the field and outside of the capital city, and serve as key middle managers working at the nexus between policy and implementation. In Uganda, <1% of eligible HIV-infected patients have initiated IPT.³ Our preliminary work has identified three barriers among DHOs to IPT uptake. First, knowledge of scientific evidence of the efficacy of IPT has not diffused among DHOs (and downstream to providers). Second, the system is already perceived as operating at capacity, and adding yet another two pills (INH and Vitamin B6) to prevent a long-term outcome is not prioritized. Third, geographic remoteness and poor infrastructure (e.g. roads and internet) dilute managerial efficacy and accountability between DHOs and the front line workforce.

To catalyze IPT implementation across Uganda, we propose to test a multi-component “SPIRIT” (Simplified INH Preventive Therapy) intervention targeting DHOs – whom we view as critical dissemination agents – in two geographical regions in Uganda. Our intervention is based on the empirically-validated PRECEDE model,⁶ which suggests that health promotion strategies are most effective when they combine: (1) “predisposing factors” comprised of knowledge, attitudes or beliefs that affect behavior; (2) “enabling factors” that facilitate change by making the behavior “easier”; and (3) “reinforcing factors” which include anticipated consequences following a behavior.⁷

[figure not shown]

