5.7.2 Sample Size & Accrual

Sample size considerations for the primary outcome of IPT uptake: In the control condition (standard of care), we anticipate 10% of eligible individuals will receive IPT. We anticipate that 50% of eligible individuals will receive IPT in the intervention condition. Assuming 12 DHO groups per arm and an extremely conservative matched pair coefficient of variation k_m of 0.4, this study will be powered at >95% (Figure 2).⁴⁴ If we more than double the anticipated rate of IPT use in the control condition to 25% (vs. 50% in the treatment condition), the power remains at >90%. Of note, unlike a traditional sample size calculation where the investigators must “enroll” to reach a desired sample size, we use routine health systems data and therefore calculate anticipated power from a fixed sample size based on the number of DHO groups. As shown in Figure 2, these power calculations are not sensitive to the number of patients enrolled in each DHO group. We expect 1,000-25,000 patients in each DHO group.

Figure 2 (right): Power calculations for the primary outcome of IPT uptake, assuming 12 DHO groups per arm and varying the outcome among the standard of care (SoC) and the number of patients

6. IPT Adherence & TB Incidence in the SPIRIT Trial

Rationale: The population health impact of our DHO intervention aimed at reducing TB depends not only on IPT prescribing, but also on adherence and completion of IPT by patients. Thus, to understand the implementation pathway, it is important to measure an adherence outcome, which we propose to assess through the analyses of INH refill visits, as metrics of long-term pill consumption. Because ART use can both affect risk for TB in HIV+ persons, and be indirectly affected by our DHO intervention, we will also measure ART refills in our sampled subset of Aim 2. As another secondary outcome, TB incidence contributes to quantifying the magnitude of the public health effect of SPIRIT.

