Primary outcome: We will examine the impact of the SPIRIT intervention on the incidence rate of TB among all HIV-positive adults at a health facility overseen by DHOs participating in the SPIRIT trial. The analysis of TB incidence in the population will mirror the primary analysis of Aim 1. Assuming an incidence rate 200 cases per 100,000 person-years in the standard of care,⁴⁵ and 10% completion of IPT (which conservatively reduces TB incidence by 40%,^{1,2} the incidence density method suggests a two-year cumulative incidence of approximately 0.38% in the control arm. Figure 4 shows the effect size that we are powered to detect when the control cumulative incidence is 0.35-0.40%.⁴⁴ Since the outcome is rare, these calculations are more sensitive to the number of patients per DHO group. However, we are relying on existing data collection systems (“blue card” forms and MoH TB clinic registries). Therefore, we anticipate capturing TB case reports on at least 3000 patients per DHO group. Assuming a control incidence of 0.38%, at least 2800 eligible patients in each DHO group, 12 DHO groups per arm, and a matched pair coefficient of variation $k_m=0.2$, we will be powered to detect 40% reduction in TB incidence in the overall population.

The analysis of TB incidence in the sub-sample of Aim 2 will mirror the analysis of IPT completion (Section 6.5.2.1). We will adjust for clustering and the sampling probability to make inferences about the target population of IPT-prescribed, HIV-infected persons in Uganda.

Figure 4: Effect size (in percent decrease in TB incidence) detected with at least 80% varying the incidence under the standard of care (SoC) and number of HIV-positive adults per DHO group. We assume 12 DHO groups per arm and a matched pair coefficient of variation $km=0.2$.

**Effect Size Detected with 80% Power
Varying the Number of HIV+ Adults
and TB incidence in the Standard of Care (km: 0.2)**

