Additional analyses: We will examine how IPT uptake varies over time by plotting the quarterly incidence rate (as described above) and the cumulative incidence (quarter-specific starts divided by quarter-specific number of adults on ART) over time by arm, region, and sex. We will also formally evaluate trends over time using TMLE to estimate parameters of a marginal structural model and using GEE [4, 14, 15]. We will also examine how DHO/DTLSs participation mediates the intervention effect with TMLE. Finally, we will conduct an “as-treated” analysis where intervention districts whose DHOs/DTLSs had poor participation in mini-collaboratives are analyzed as receiving the standard-of-care (i.e., control).

3 Secondary outcome: HIV-associated TB incidence

We will also examine the impact of the SEARCH-IPT intervention on “HIV-associated TB incidence”: the rate at which persons in active HIV care are diagnosed with TB disease in districts overseen by DHOs participating in the SEARCH-IPT trial. Thus, the target and analytic population include all persons in active HIV care, regardless of their age, sex, ARV regimen, IPT eligibility, or IPT uptake. As with the primary endpoint, TB incidence will be measured over 8 quarters (starting Q1-2019 in the Southwest and in Q2-2019 in the East and East-Central).

Data source: For each *district*, aggregate data on the total number of TB diagnoses among persons in active HIV care and the total number of persons in active HIV care *in each quarter* will be extracted from the Ministry of Health HMIS database. While data on the active size are available by 1st/2nd/3rd line ARV regime, all analyses will pool ARV regime.

Missing data: There is no reason to believe data will be differentially captured by arm. As before, we are unable to distinguish between missing values and 0 persons diagnosed with TB. Therefore, if data are missing on TB cases for a given district-quarter, we will assume there were 0 cases in that district-quarter. However, if for a given district, data on TB cases are missing for all quarters, we will exclude that district from the analysis.

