3. How strong is the evidence that INH prevents death in HIV-infected patients? With responses: 1: very weak; 2: weak; 3: mixed; 4: strong; 5: very strong.
4. How much risk of INH drug resistance is there if a person develops active TB after completing IPT? With responses: 1: no risk of INH resistance; 2: low risk; 3: moderate risk; 4: high risk; 5: very high risk.
5. How difficult is it for providers in this district to add INH to standard care for HIV-infected people in order to prevent TB? With responses: 1: very easy; 2: easy; 3: neither hard nor easy; 4: difficult; 5: very difficult.
6. How hard is it to influence changes in practice among frontline providers around TB management? With responses: 1: very easy; 2: easy; 3: neither hard nor easy; 4: difficult; 5: very difficult.

6.3 Power calculations:

Sample size and power calculations were based off the standard formulas for one-sided tests in cluster randomized trials with an incidence rate endpoint [1]. As a conservative approximation, these calculations considered the randomization groups to be the independent unit. We also expect these calculations to be conservative, because of the precision gained through covariate adjustment in the analysis.

We estimated 14 groups (7 groups/arm) would provide 80% power to detect at least a 10% absolute increase in IPT uptake (the primary outcome) from 22 per 100 person-years under the control, assuming a coefficient of variation of $k = 0.25$ and $\approx 21,500$ person-years of follow-up in each group. As shown in the following Figure, these calculations are fairly insensitive to expected amount of follow-up in group. If uptake is greater than expected (e.g., 30 per 100 person-years) under the control, we anticipate remaining well-powered to detect at least a 13.5% increase in uptake.

References

- [1] R.J. Hayes and L.H. Moulton. *Cluster Randomised Trials*. Chapman & Hall/CRC, Boca Raton, 2009.
- [2] L.B. Balzer, M.L. Petersen, M.J. van der Laan, and the SEARCH Consortium. Adaptive pair-matching in randomized trials with unbiased and efficient effect estimation. *Statistics in Medicine*, 34(6):999–1011, 2015. doi: 10.1002/sim.6380.
- [3] K.J. Rothman, S. Greenland, and T.L. Lash. *Modern Epidemiology*. Lippincott Williams & Wilkins, Philadelphia, 3rd edition, 2008.

[4] M. van der Laan and S. Rose. *Targeted Learning: Causal Inference for Observational and Experimental Data*. Springer, New York Dordrecht Heidelberg London, 2011.

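### The stated power for a 40% TB reduction rests on 12 groups per arm when 7 were randomised, and is never set beside the 9–17% reduction that the protocol's own inputs imply

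*Protocol*

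**What the plan says.** Protocol 6.5.2.2 builds the control risk from three inputs: "Assuming an incidence rate 200 cases per 100,000 person-years in the standard of care", "and 10% completion of IPT (which conservatively reduces TB incidence by 40" per cent, and two years of follow-up. The result is about 0.38%. For 12 groups per arm, at least 2,800 patients per group and km = 0.2, it then concludes that "we will be powered to detect 40% reduction in TB incidence in the overall population". The caption of Figure 4 gives the power as 80%. The introduction uses the same efficacy: "IPT reduces TB incidence by 40" per cent.

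Elsewhere the protocol gives what is needed to project the intervention arm. Section 5.7.2 says "We anticipate that 50% of eligible individuals will receive IPT in the intervention condition". Section 6.5.2.1 takes 44% completion among starters under standard of care and sizes for a 40% increase in it.

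Protocol 5.2 and SAP section 1 have 7 groups per arm. SAP section 3 tests TB one-sided at 5% and says "TB incidence will be measured over 8 quarters (starting Q1-2019 in the Southwest and in Q2-2019 in the East and East-Central"). SAP 6.3 gives power for IPT uptake only; the SAP has no TB detectable effect.

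**The concern.** The formula that produced 0.38% for control was not applied to the intervention arm, so nothing shows whether a 40% population reduction is plausible. It equals the full individual-level effect of IPT, as if everyone in the intervention arm were protected and nobody in control, although the same paragraph gives control 10% completion. The number of groups behind it is also not the number randomised.

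Lowering TB incidence is part of the overall objective in Protocol section 2, and it is formally tested in SAP section 3. The protocol sentence is the only statement in the text of what the TB comparison can detect. A reader who relied on it could take a non-significant result as evidence that SPIRIT does not affect TB, when the comparison had little chance of showing the effect the plan's own figures predict.

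**Working it through.** **1. Control risk.** 0.002 × 2 × (1 − 0.10 × 0.40) = 0.00384, or 1 − exp(−0.00384) = 0.383%. This matches the stated 0.38%.

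**2. The stated 40%.** Pair-matched cluster formula for proportions, groups per arm:

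c = 2 + (z_α + z_β)² × [p0(1−p0)/m + p1(1−p1)/m + km²(p0² + p1²)] / (p0 − p1)²

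With p0 = 0.0038, p1 = 0.6 × 0.0038 = 0.00228, m = 2,800, km = 0.2, two-sided 5% and 80% power:
- bracket = 1.352e-6 + 0.812e-6 + 0.786e-6 = 2.950e-6
- (p0 − p1)² = 2.310e-6
- c = 2 + 7.849 × 1.277 = 12.02

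At 12 groups per arm, power is 79.9%, so the protocol's figure reproduces. The protocol does not name its formula or sidedness for TB. This version fits; a one-sided matched test gives 87.6%.

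**3. The same claim with 7 groups per arm.** At m = 2,800, power for a 40% reduction is 51% two-sided and 63% one-sided.

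**4. Reduction implied by the protocol's inputs.** Reduction = 1 − (1 − 0.40 × completion in intervention)/(1 − 0.40 × 0.10).
- 50% start and all complete: 1 − 0.80/0.96 = 16.7%.
- 50% start and 61.6% of them complete (44% × 1.4, reading the 40% increase as relative), so 30.8% overall: 1 − 0.8768/0.96 = 8.7%.
- 100% complete: 1 − 0.60/0.96 = 37.5%.

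If the 10% in control is instead read as starts with 44% completing (4.4%), the second line becomes 1 − 0.8768/0.9824 = 10.7%, still inside 9–17%.

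All these assume direct protection only, in force from the first day of the window. That timing is generous: TB is counted from the quarter in which IPT starts begin to be counted, so coverage builds up inside the window.

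**5. Detectability with 7 groups per arm** (same formula, km = 0.2, p0 = 0.38%; each cell one-sided / two-sided):

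| Patients per group | Detectable reduction, 80% power | Power for 16.7% | Power for 8.7% |
|---|---|---|---|
| 2,800 | 48.8% / 53.9% | 19% / 12% | 10% / 6% |
| 10,750 | 34.7% / 38.5% | 30% / 20% | 14% / 8% |
| 25,000 | 30.8% / 34.2% | 35% / 24% | 16% / 9% |
| No limit | 27.5% / 30.5% | 42% / 30% | 18% / 11% |

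The 2,800 is the protocol's floor and 25,000 the top of its expected range (Protocol 5.7.2). The 10,750 is SAP 6.3's 21,500 person-years per group divided by two years. That figure is for uptake, which is measured in two clinics per district, so district-wide TB numbers may be larger.

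Example for the first row: p1 = 0.003167, bracket = 3.458e-6, (p0 − p1)² = 4.011e-7, √(5 × 4.011e-7/3.458e-6) = 0.76. Power is Φ(0.76 − 1.645) = 19% one-sided and Φ(0.76 − 1.96) = 12% two-sided.

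**6. The SAP's 7 + 40 independent units** (one-sided, t with 45 df, unadjusted). The documents give no TB coefficient of variation for these units. I assumed values from 0.2 in both arms up to 0.25 for collaboratives and 0.55 for control districts, with each control district holding 7/40 of a group's patients. The detectable reduction is 39.6–44.5% at 2,800 per group, 21.4–30.3% at 25,000 and 17.6–27.9% with no limit. Power for 16.7% is 21–25%, 36–59% and at most 75%.

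**The case against.** The strongest reply is that 40% is a detectable effect at a minimum group size, not a target. The protocol ties it to at least 2,800 patients per group, says the calculation is sensitive to that number, and refers to Figure 4 for other values, which cannot be seen here. This stands, and it rules out some stronger readings. Because 40% exceeds the 37.5% ceiling, a reader might infer that the trial could see only an effect its intervention cannot produce, or that the TB question cannot be answered at all. The documents do not support that: at 25,000 patients per group the detectable reduction is below 37.5%, with 7 per arm or 7 + 40 units.

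The ceiling is also not firm. The protocol calls 40% efficacy conservative, and above 0.40/0.94 = 42.6% a 40% reduction becomes possible at full completion. At that efficacy, though, 50% against 10% completion gives only 17.8%; reaching 40% would need 0.40/0.44 = 91% efficacy. Lower transmission and better ART adherence, both mentioned in the protocol, could add benefit, and TMLE adjustment could add precision. Neither is quantified for TB.

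A reader might also put the SAP's uptake contrast, "80% power to detect at least a 10% absolute increase in IPT uptake (the primary outcome) from 22 per 100 person-years under the control", through the formula and report an expected TB reduction of about 3%. That contrast is what the trial can detect, not what it expects, and SAP section 2 says that starts are not uniform over time. The 3% should not be used as an expected effect.

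Finally, SAP section 3 already plans two-sided 95% intervals, and no text says that a null will be read as no effect. Both are true. The misreading is a risk, not a stated plan.

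**Conclusion.** The concern holds in a limited form. The 40% claim as written is not supported by the randomised design: at the group size it cites, power is 51–63%, not 80%. The more important gap is between what can be detected and what is implied. The protocol's inputs imply a 9–17% reduction. The detectable reduction is 49–54% at 2,800 patients per group and 31–34% at 25,000 under the matched formula, and it stays above 16.7% in every unadjusted scenario run, including the 7 + 40 units with unlimited group size. A null TB result could not be told apart from the implied effect.

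This rests on 40% efficacy, 10% completion in control, direct protection only, a control risk of 0.38% and km = 0.2. The 7 + 40 figures also rest on my assumed coefficients of variation. It does not show that TB incidence is uninformative: a large reduction could still be detected with large groups.

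**What to change.** In Protocol 6.5.2.2, restate the detectable TB reduction for 7 groups per arm, the SAP's one-sided test and the expected group sizes. Beside it, give the implied 9–17% reduction with its assumptions: direct protection only, and full coverage from the start of the window.

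In SAP section 3, which contains no 40% figure to replace, add two statements: that the TB comparison is not powered for the implied effect, and that a non-significant result will be read from its confidence interval and not as evidence of no effect on TB. Date the addition, because SAP 6.1 records that the TB analysis was locked before unblinding in version 1.0.

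No new analysis is needed. A start of TB counting lagged by two quarters would change little, and the planned analysis excluding the pre-lockdown period already looks at later TB. The cost is wording and a short recalculation; the stated TB power becomes less favourable.

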6.5.3 Sampling Approach & Sample Size Considerations

In our sampling approach for adherence measures and intensified TB case finding, we first stratify on the DHO randomization group. Then within DHO groups we will sample a minimum of thirty patients who are prescribed INH. To preserve generalizability, the sampling of patients may be further stratified by facility characteristics (e.g. size, DHO, SPC availability) and may be staggered across study time. We aim to perform chart review among 800 patients total, 400 per SPIRIT trial arm.

7. Evaluate the impact of business and leadership training on management and leadership skills among SPIRIT intervention vs. control DHOs.

Rationale: The SPIRIT intervention seeks to increase routine, appropriate use of isoniazid at the clinic systems level, in part by providing leadership and management training during teaching mini-collaboratives. As a result we hypothesize that self-reported confidence in DHO leadership and management skills will be greater in intervention than control DHOs.

7.1. Teaching Mini-Collaborative Business Leadership and Management training

As noted in the SPIRIT-1 intervention (see Section 5.3.1.), additional training at the Teaching Collaboratives (and the Reporting Collaboratives) includes business and management training provided by business leaders, that aim to assist the DHOs and the District TB Supervisors in overseeing any new or ongoing initiatives to improve IPT implementation. DHOs are trained as clinicians and public health officers, but their qualifications and training do not include formal leadership and management training. Through additional business training, the SPIRIT intervention seeks to increase DHO leadership and management competency, thus improving implementation of IPT.

7.2. Measures

Measures obtained will include:

1. The Leadership Business Description Questionnaire (LBDQ),⁴⁶ adapted for the DHOs to provide self-reported quantitative assessment of their leadership and management skills, and measured at the completion of the SPIRIT trial, Phase 1.
2. Qualitative Key Informant Interviews (KII): Management and Leadership assessments, using interview guides based on the World Management Survey⁴⁷, implemented among DHOs participating in qualitative interviews at the completion of the SPIRIT trial, Phase 1.

7.3. Outcomes

The primary outcome for the analysis of business training is the quantitative assessment of leadership and management skills as measured by the Leadership Business Description Questionnaire in intervention vs. control DHO groups at the completion of the SPIRIT trial, Phase 1. Qualitative outcomes will include DHOs' perceptions of business training content and impact of the business training on attitudes and practices.

7.4. Data Management & Statistical Considerations

7.4.1. Data Collection & Management

Staff will conduct the adapted LBDQ survey and KII at the completion of the SPIRIT Trial, Phase 1. Data from these surveys will be entered and transferred via a secure electronic transfer to our data center facility in Kampala and stored on a secure server.

7.4.2. Analysis

Analyses will evaluate the impact of the SPIRIT Phase 1 intervention on LBDQ scores between randomization arms using TMLE, implemented analogously to the primary endpoint of IPT uptake (see Section 5.7 above).

8. Costs & Cost-Effectiveness of SPIRIT

In order to generate evidence that can address key questions concerning optimal resource allocation and provide guidance to policymakers, we will use rigorous methods to determine the costs of the SPIRIT intervention and assess its cost-effectiveness – particularly the cost per person initiating and completing IPT as well as the costs per TB case averted and disability-adjusted life years (DALYs) averted.

8.1 Costs

We will use standard micro-costing techniques to measure the cost of each component of the SPIRIT intervention. This will include costing of training activities and efforts made to transfer knowledge to DHOs in meetings; costs associated with utilizing opinion leaders to teach DHOs; costs of the SPC for administering INH, SMS system development and implementation, and other communication efforts; and costs of biannual meetings held with DHOs. This costing process will quantify the resource and associated unit costs required to deliver each intervention step, organized in standard expenditure categories—personnel, supplies, equipment, services (e.g. electricity), space, and overhead. Costs will be allocated to each intervention step to the extent possible and review of the division of shared resources and staff time, noting and reporting uncertainties in these divisions. Information required to determine costs will be obtained through examination of expenditure records, discussion with program managers and staff including pharmacy, care delivery labs and observation of service delivery for a sample of patients. Focused “time and motion” studies to allocate staff time across tasks within and outside the intervention will also be carried out to properly account for health care workers’ time devoted to the intervention. Donated and subsidized resources will be appraised at market value. We will assess costs from the societal perspective, i.e. including costs to patients and their family members in the form of out-of-pocket expenditures and also lost productivity. To assess costs incurred by patients, we will administer short questionnaires to patients selected for participation in the Aim 2 sub-sample at intervention and control facilities that elicit their expenditures for transportation to receive treatment and the value of the time lost in accessing care by clients and accompanying family members and time lost due to illness.

